10.3.2 Laboratory Test Assessments

Any abnormal laboratory test result considered clinically significant by the Investigator must be recorded.

10.3.2.1 Serum Chemistry

Serum chemistry tests include: LDH, glucose, total protein, albumin, BUN or urea, creatinine, ALT, AST, serum alkaline phosphatase, direct and total bilirubin, sodium, potassium, chloride, HCO₃, calcium, magnesium, and uric acid. Serum Chemistry is to be obtained as outlined in Section 10.0. Three (3) ml of blood will be drawn for serum chemistry, exclusive of TSH. In addition, TSH, free T3, free T4, ACTH and total cortisol will also be obtained as described in Section 10.0 to monitor endocrine side effects of nivolumab or ipilimumab. Lastly, AFP for tumor marker assessment will also be monitored.

10.3.2.2 Hematology

CBC with differential are to be obtained as outlined in Section 5.1. Complete Blood Count (CBC) with differential includes hemoglobin, hematocrit, white blood cells, platelets, neutrophils, lymphocytes, eosinophils and monocytes. PT and PTT will be drawn at baseline and prior to surgery or future procedures. Additional draws must be incorporated to monitor recovery from any hematologic laboratory AE. Two and a half (2.5) ml blood will be drawn for hematology.

10.3.2.3 Tumor Tissue

Available tumor tissue, obtained at pre-treatment and the time of surgical resection or biopsy (if unresectable) will be collected for immune monitoring studies as described below (Section 10.3.3).

10.3.3 Immune Tests

The Immunotherapy Platform will perform immune monitoring, including but not limited to evaluation of CD4 and CD8 T cells in peripheral blood and available tumor samples as previously published [52-59]. All samples will be collected and analyzed as per a separate IRB-approved lab protocol.

All blood collection will be compliant with institutional safety standards and will not exceed the maximum blood draw per venipuncture policy.

10.3.4 Evaluation of Clinical Responses

10.3.4.1 Efficacy Assessments

Progression-free survival (PFS) and objective response rate (ORR), each based on RECIST 1.1 criteria, are two of the primary efficacy assessments of this study. See Sections 12.2.2.1 and 12.2.2.4 for the definitions of ORR and PFS, respectively.

10.3.4.2 Criteria for Progression and Responses

Evaluation of response will follow the Response Evaluation Criteria in Solid Tumors (RECIST) Guidelines. All tumor measurements must be recorded in centimeters.

- Target Lesions:

All measurable lesions up to a maximum of five lesions per organ and 10 lesions in total, representative of all involved organs, should be identified as target lesions and recorded and measured at baseline. Target lesions should be selected on the basis of their size (those with the longest diameter) and their suitability for accurate repeated measurements (either by imaging techniques or clinically). A sum of the longest diameter for all target lesions will be calculated and reported as the baseline sum longest diameter. The baseline sum of longest diameters will be used as the reference by which the objective tumor response is characterized.

- Non-target Lesions:

All other lesions (or sites of disease) should be identified as non-target lesions and should also be recorded at baseline. Measurements of these lesions are not required, but the presence or absence of each should be noted throughout follow-up.

- Evaluation of Target Lesions:

- Complete Response: The disappearance of all target lesions.
- Partial Response: At least a 30% decrease in the sum of the longest diameter of target lesions, taking as reference the baseline sum longest diameter.
- Progressive Disease: At least a 20% increase in the sum of the longest diameter of target lesions, taking as reference the smallest sum longest diameter recorded since the treatment started or the appearance of one or more new lesions.
- Stable Disease: Insufficient shrinkage to qualify for partial response, or insufficient increase to qualify for progressive disease, taking as reference the smallest sum longest diameter since the treatment started.

- Evaluation of Non-target Lesions:

- Complete Response: The disappearance of all non-target lesions.

- Incomplete Response/Stable Disease: The persistence of one or more non-target lesion(s)
- Progressive Disease: The appearance of one or more new lesions and/or unequivocal progression of existing non-target lesions.
- Evaluation of Best Overall Response: (see Table 4)

The best overall response is the best response recorded from the start of treatment until disease progression/recurrence (taking as reference for progressive disease the smallest measurements recorded since the treatment started).

Table 4. Evaluation of Best Overall Response

Target Organ Lesions	Non-Target Organ Lesions	New Lesions	Overall Response
CR	CR	No	CR
CR	Incomplete response/SD	No	PR
PR	Non-PD	No	PR
SD	Non-PD	No	SD
PD	Any	Yes or No	PD
Any	PD	Yes or No	PD
Any	Any	Yes	PD

10.3.4.3 Immune related Response Criteria (irRC)

Table 5. irRC outcome measures [64]

New, measurable lesions	Incorporated into tumor burden
New, non- measurable lesions	Do not define progression (but precludes irCR)
Non-index lesions	Contribute to defining irCR (complete disappearance is required)
Complete response (CR)	Disappearance of all lesions in two consecutive observations not less than 4 weeks apart
Partial response (PR)	$\geq 50\%$ decrease in tumor burden compared with baseline in two observations at least 4 weeks apart
Stable disease (SD)	50% decrease in tumor burden compared with baseline cannot be established nor 25% increase compared with nadir
Progression of disease (PD)	$\geq 25\%$ increase in tumor burden compared with nadir (at any single time point) in two consecutive observations at least 4 weeks apart

Note: According to the irRC, disease progression of non-index lesions or appearance of new non-measurable lesions will not classify the subject as PD, and therefore the subject may stay in the study if it is the in the subject's best interest. A confirmatory tumor assessment may be performed no less than 4 weeks after the first indication of progression to provide additional data for the investigator to decide if the subject should stay in the trial or be discontinued due to clinical progression based on the investigator's decision.

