2.0 OBJECTIVES

Primary Objective:

1. To evaluate the safety and tolerability of therapy with nivolumab alone or nivolumab + ipilimumab in resectable HCC in the context of presurgical therapy.

Note: As of January 8, 2020, 30 patients have been enrolled and 27 patients have been randomized. The PI decided to stop enrollment since the study has reached its primary endpoint of safety.

Secondary Objectives:

1. To assess the efficacy of presurgical nivolumab alone or nivolumab + ipilimumab therapy in HCC by estimating the objective response rate (ORR) and time to progression (TTP) per RECIST 1.1 progression-free survival (PFS).

Exploratory Objectives:

1. To assess the *immunological/biomarker changes* in tumor tissues and peripheral blood in response to nivolumab alone or nivolumab + ipilimumab in HCC therapy (pre- vs post-treatment), and explore any potential association between these biomarker measures and antitumor response and immune-related response criteria (iRC) assessed by MD Anderson Department of Diagnostic Imaging.

[figure not shown]

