After finishing the last treatment, hepatic resection or biopsy will occur on day 1 of week 7 (+/- 7 days). We will obtain surveillance scans (MRI of abdomen and pelvis with/without contrast, and CT chest with/without contrast of chest) 8 weeks after surgery. Patients who show significant progression of disease post-operatively will be taken off study and an optional biopsy will be taken at that time for immunological analysis.

Patients who complete the study or discontinue study treatment should be scheduled for an end of treatment visit (EOT) as soon as possible. All patients who complete the study or discontinue treatment will have a safety follow-up visit 30 (+/- 14 days) after the last dose of study drug or surgery, whichever comes last. Please refer to **Figure 2** below for the study design.

Patients will receive baseline staging studies with CT or MRI and be assessed for treatment response by scans: MRI or CT of abdomen and pelvis with/without contrast, and CT chest with/without contrast of chest (according to RECIST 1.1 and irRC) at week 6 (+/- 7 days). Each patient will have post-surgical (day 1 of week 11 +/- 7 days), staging studies as above. Subsequently, restaging will be carried out every 12 weeks unless, in the investigators' opinion, follow-up intervals need to be shorter. Studies to confirm a complete response or document progressive disease will be performed as needed. Patients will be allowed to continue study therapy after initial investigator-assessed RECIST 1.1/irRC-defined progression if they are deemed by the investigator to be deriving clinical benefit and tolerating study drug(s), as described in Section 8.3.

[figure not shown]

Figure 2. Study Design of preoperative nivolumab alone or in combination with ipilimumab. There are 2 arms to this study: A) Nivolumab monotherapy in resectable HCC; B) Combination nivolumab plus ipilimumab in resectable HCC.

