- h. Blood will be collected prior to dose one (C1D1), Cycle 2 and 3 (before the 2nd and 3rd dose of Nivolumab), at time of surgery (C4D1), at 8 weeks after surgery (C6D1), at every restaging thereafter (q12 weeks), and finally at treatment discontinuation (confirmed progression or end of therapy).
- i. Screening tumor imaging will be performed within 28 days prior to allocation for confirmation of baseline measurable disease per RECIST 1.1 as required prior to subject allocation, then at time of surgery. After surgery, imaging will be repeated and therapy starts at C7D1, then surveillance imaging will be repeated q12W (72 \pm 7 days).
- j. Biopsies will be required pre-treatment and at time of surgery.
- k. The first on-study imaging time point will be performed at 6 weeks around time of surgery (42 \pm 7 days) calculated from the date of allocation and then 8 weeks after surgery, and will continue to be performed q12W.
- l. SAEs will be followed through 100 days following cessation of treatment, or 100 days following cessation of treatment if the subject initiates new anticancer therapy, whichever is earlier.
- m. HBV/HCV viral loads (for subjects who have known history of chronic infection) will be measured during screening, then at C1D1, at time of surgery (C4D1), at 8 weeks after surgery (C6D1), at every restaging thereafter (q12 weeks), and at time of discontinuation.
- n. The following imaging studies are required at screening, at time of surgery, at 8 weeks after surgery, then at every restaging thereafter (q12 weeks): CT chest with or without contrast; MRI of abdomen and pelvis with or without contrast unless patient has contraindication for MRI or severely claustrophobic.
- o. Every time imaging is done for re-staging (q12 weeks).

Trial Period:	Screening Phase	Treatment Cycles. 3 cycles (2-Week Cycles) planned before surgery then after surgery (4-Week Cycles), patients may receive up to 2 years of therapy depending on response and every restaging scans every 12 weeks							End of Treatment	Post-treatment		
Title:	Screening				Surgery				Discontinue	Safety Follow-up ^l	Follow-Up Visits	Survival Follow-Up ^a
Treatment Cycle/Day:	0	C1D1	C2D1	C3D1	C4D1	C5D1	C6D1	C7+D1	At time of discon	30 days post last dose	Every 9 weeks post-discon	Every 12 weeks
Scheduling Window (Days) ^b	-28 to -1	±3	±3	±3	±7	±3	±3	±3	±3	±7	±7	±7

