10.3.4.4 Time -to- Event Assessment of Response

Time to Response: From the start of study drug to the first observation of a response (the first of two confirmatory measurements).

Duration of Response: From the first observation of a response (the first of the two confirmatory statements) to the first observation of progressive disease, or to death due to any cause, or early discontinuation of treatment due to progressive disease.

Time to Progression: From the start of study drug to the first evidence of progression.

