12.0 STATISTICAL METHODOLOGY

12.1 Preliminaries and Objectives

This is a randomized, pilot trial of nivolumab (Arm A) or nivolumab + ipilimumab (Arm B) as pre-operative treatment for patients with hepatocellular carcinoma who are eligible for surgical resection. Each patient in both Arms A and B will be given nivolumab at 240 mg every 2 weeks

for a total of 6 weeks. Patients in Arm B will additionally be treated concurrently with ipilimumab at 1mg/kg every 6 weeks. No dose increases or reductions will be allowed for nivolumab or ipilimumab. Surgical resection or post-treatment biopsy will occur within 4 weeks after finishing the last cycle of therapy. The rationale is that nivolumab and ipilimumab activate the immune system via distinct mechanisms and therefore, the combination of nivolumab and ipilimumab may result in synergistic activation of the immune system against hepatocellular carcinoma. The primary objective is to assess the safety and tolerability of nivolumab +/- ipilimumab. Secondary objectives include estimating the ORR and TTP of the 2 different arms. Exploratory objectives include evaluating the pre- and post-treatment immunological changes in tumor tissues and peripheral blood.

As of January 8, 2020, 30 patients have been enrolled and 27 patients have been randomized. The PI decided to stop enrollment since the study has reached its primary endpoint of safety.

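### On the scheduled scans, a patient resected on time cannot have a confirmed irRC response before surgery, so the irRC part of the exploratory biomarker association is not evaluable as written

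*Combined protocol and SAP*

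**What the plan says.** Section 2.0 includes, among the exploratory aims, to "explore any potential association between these biomarker measures and antitumor response and immune-related response criteria (iRC"). Section 5.3 has patients scanned for response "according to RECIST 1.1 and irRC) at week 6 (+/- 7 days"), so an irRC reading before surgery is intended.

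Table 5 in Section 10.3.4.3 sets the irRC rules. Partial response is a fall of 50% or more, defined as a "decrease in tumor burden compared with baseline in two observations at least 4 weeks apart". Complete response is "Disappearance of all lesions in two consecutive observations not less than 4 weeks apart".

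On timing, note k to the Arm A schedule in Section 10.0 says: "The first on-study imaging time point will be performed at 6 weeks around time of surgery", with a window of 42±7 days from allocation. Section 5.3 says that "hepatic resection or biopsy will occur on day 1 of week 7 (+/- 7 days"). Section 12.1 differs: "Surgical resection or post-treatment biopsy will occur within 4 weeks after finishing the last cycle of therapy".

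Section 10.3.4.4 also relies on a repeat measurement. Time to response runs "From the start of study drug to the first observation of a response (the first of two confirmatory measurements").

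**The concern.** The week-6 visit is meant to yield an irRC classification, yet irCR and irPR each need a second observation that the schedule does not supply before the tumour is taken out. A patient whose tumour burden has more than halved at week 6 would, under Table 5, be left as stable disease or unclassified. The second scheduled observation comes after resection. Read literally, it would confirm a week-6 reduction because the lesion is no longer there, and two clear postoperative scans would satisfy the irCR definition in a patient whose tumour never shrank on drug. No section says how scans after resection are to be scored.

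At stake is the comparison of biomarkers with irRC response. It would have either an empty responder group or one that marks who had surgery. Section 12.6 does not settle this: it tests immune measures against a binary overall treatment response without naming the criterion or the scan.

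**Working it through.** **The plan's own response figure.** Section 12.6 states that 15 patients give more than a 90% chance of at least one response at a true rate of 15%. The check is 1 − 0.85^15 = 0.913, which agrees. Section 12.2.2.1 defines response by RECIST 1.1, so Table 5 confirmation does not enter this figure.

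**Inputs, in days from allocation.**
- Earliest week-6 scan: 42 − 7 = 35 (Section 10.0, note k).
- First dose: up to 3 days after allocation (Section 10.0, note b).
- Dosing visits: ±3 days; third dose nominally 28 days after the first.
- Resection: nominally 42 days after the first dose, ±7 (Section 5.3).
- Interval needed for irCR or irPR: 28 days (Table 5).

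**Longest possible gap from scan to surgery** = latest surgery − earliest scan.

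| Surgery rule | Latest surgery | Longest gap | Gap at nominal dates |
|---|---|---|---|
| Section 5.3 | 3 + 42 + 7 = 52 | 52 − 35 = 17 | 42 − 42 = 0, or 42 − 35 = 7 if the scan is at the start of week 6 |
| Section 12.1, counted from the third dose | 3 + 28 + 3 + 28 = 62 | 62 − 35 = 27 | 56 − 42 = 14 |
| Section 12.1, counted from the end of the third 2-week cycle | 3 + 42 + 3 + 28 = 76 | 76 − 35 = 41 | 70 − 42 = 28 |

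Under Section 5.3 the gap is always below 28 days. Under the shorter reading of Section 12.1 it still is. Only the longer reading leaves room, and no second presurgical scan is scheduled there either.

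**First scan after surgery.** Section 5.3 gives both day 1 of week 11 and 8 weeks after surgery. Week 11 falls 70 − 42 = 28 to 70 − 35 = 35 days after the week-6 scan at nominal dates. Eight weeks after surgery falls (42 + 56) − 42 = 56 days after it. Either can meet the 28-day interval, but with the resected lesions gone.

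**Which parts of the exploratory objective use Table 5.**
- Pre/post biomarker change: no.
- Association with antitumour response by RECIST: no. Section 10.3.4.2 states no confirmation interval.
- Association with irRC: yes.

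**The case against.** The best counter-argument is that the schedule is not the whole protocol. Section 7.0 lets surgery wait until an adverse event has settled, and Section 12.2.1 counts a delay as an extreme toxicity only beyond 3 months, so shorter delays are foreseen. Section 5.3 allows imaging as needed to confirm complete response or document progression. The longer reading of Section 12.1 could fit a second scan. All of this stands, and it rules out a stronger inference that a reader might draw: that no patient could ever be a confirmed presurgical irRC responder. It does not help a patient resected within the Section 5.3 window, for whom 28 days do not exist, and the as-needed provision does not name partial response.

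A reader might also infer that the exploratory objective fails as a whole. The documents do not support that: two of its three parts do not use Table 5, and Section 2.0 does not say that the irRC response must be presurgical or confirmed. Nor can the effect be put as zero responders among the 27 randomized patients. The documents give no count of patients resected, and Section 5.3 itself expects 1 to 3 of 30 not to reach resection.

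Finally, the protocol does not say that a clear postoperative scan will be scored as irCR; it is silent. That is fair, but Table 5 taken literally permits that scoring and nothing in the text excludes it. Time to response and duration of response are defined in Section 10.3.4.4 but are not among the objectives, listed endpoints or planned analyses, so their share of the problem is minor.

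**Conclusion.** The point holds for patients resected within the Section 5.3 window and scanned as scheduled. They have one on-study scan before surgery, at most 17 days ahead of it against 28 required, so a confirmed presurgical irCR or irPR cannot arise. The irRC component of the exploratory association is not evaluable as written. The primary safety endpoint, pre/post biomarker change, association with RECIST response and the more-than-90% figure are untouched. This rests on Table 5 being applied as worded, on surgery taking place on time, and on no unscheduled presurgical scan. The size of the problem in patients cannot be given from the documents.

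**What to change.** In Section 10.3.4.3, state that presurgical irRC response is classified on the single week-6 scan against baseline and reported as unconfirmed. Percent change in tumour burden at week 6 is an alternative that needs no responder category. Add that scans after resection do not count towards irCR or irPR and serve only to detect recurrence or progression. Align the two-measurement wording in Section 10.3.4.4.

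Do not move RECIST ORR to week 6 as part of this change: Section 12.2.2.1 takes best response after 12 weeks on therapy and Section 12.6 reviews response at week 14, and moving it would redefine a secondary endpoint. Those two timepoints should instead be reconciled with each other and with a stated rule for how scans after resection count.

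Three timing conflicts also need reconciling: surgery in Section 5.3 against Section 12.1; the first postoperative scan at week 11 against 8 weeks after surgery; and note k of the Arm B schedule, which gives 8 weeks alongside 42±7 days.

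The irRC change is wording only and needs no new scans or patients, so it remains possible with enrollment closed. It should be made before irRC responders are classified, because the study is open-label. The cost is that the irRC responses are unconfirmed and must be presented as such.

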10.3.4.4 Time -to- Event Assessment of Response

Time to Response: From the start of study drug to the first observation of a response (the first of two confirmatory measurements).

Duration of Response: From the first observation of a response (the first of the two confirmatory statements) to the first observation of progressive disease, or to death due to any cause, or early discontinuation of treatment due to progressive disease.

Time to Progression: From the start of study drug to the first evidence of progression.

11.0 ADVERSE EVENT REPORTING

11.1 Serious Adverse Event Reporting (SAE) for M. D. Anderson-sponsored IND Protocols

An adverse event or suspected adverse reaction is considered “serious” if, in the view of either the investigator or the sponsor, it results in any of the following outcomes:

- Death
- A life-threatening adverse drug experience – any adverse experience that places the patient, in the view of the initial reporter, at immediate risk of death from the adverse experience as it occurred. It does not include an adverse experience that, had it occurred in a more severe form, might have caused death.
- Inpatient hospitalization or prolongation of existing hospitalization
- A persistent or significant incapacity or substantial disruption of the ability to conduct normal life functions.
- A congenital anomaly/birth defect.

Important medical events that may not result in death, be life-threatening, or require hospitalization may be considered a serious adverse drug experience when, based upon appropriate medical judgment, they may jeopardize the patient or subject and may require medical or surgical intervention to prevent one of the outcomes listed in this definition. Examples of such medical events include allergic bronchospasm requiring intensive treatment in an emergency room or at home, blood dyscrasias or convulsions that do not result in inpatient hospitalization, or the development of drug dependency or drug abuse (21 CFR 312.32).

- Important medical events as defined above, may also be considered serious adverse events. Any important medical event can and should be reported as an SAE if deemed appropriate by the Principal Investigator or the IND Sponsor, IND Office.
- All events occurring during the conduct of a protocol and meeting the definition of a SAE must be reported to the IRB in accordance with the timeframes and procedures outlined in “The University of Texas M. D. Anderson Cancer Center Institutional Review Board Policy for Investigators on Reporting Unanticipated Adverse Events for Drugs and Devices”. Unless stated otherwise in the protocol, all SAEs, expected or unexpected, must be reported to the IND Office, regardless of attribution (within 5 working days of knowledge of the event).
- **All life-threatening or fatal events**, that are unexpected, and related to the study drug, must have a written report submitted within **24 hours** (next working day) of knowledge of the event to the Safety Project Manager in the IND Office.

- Unless otherwise noted, the electronic SAE application (eSAE) will be utilized for safety reporting to the IND Office and MDACC IRB.
- Serious adverse events will be captured from the time of the first protocol-specific intervention, until 100 days after the last dose of study drug, unless the participant withdraws consent. Serious adverse events must be followed until clinical recovery is complete and laboratory tests have returned to baseline, progression of the event has stabilized, or there has been acceptable resolution of the event.
- Additionally, any serious adverse events that occur after the 100 day time period that are related to the study treatment must be reported to the IND Office. This may include the development of a secondary malignancy.

